ART	Antiretroviral therapy
AUDIT-C	Alcohol Use Disorders Identification Test – Consumption
CRF	Case report form
Grade 3/4 hepatotoxicity	ALT or ALT >3 x ULN and symptoms (nausea, vomiting, jaundice, or fatigue) OR ALT or AST >5 x ULN
NIAAA heavy drinking	Men: ≥ 4 drinks/day or ≥ 14 drinks/week; Women: ≥ 3 drinks/day or ≥ 7 drinks/week
INH	Isoniazid
IPT	Isoniazid preventive therapy
EMM	Electronic medication monitoring
PEth	Phosphatidylethanol
TST	Tuberculin skin test
ULN	Upper limit of normal

Alcohol users are considered at high risk for INH-related hepatotoxicity, based on an early study of IPT in which any and daily alcohol use were associated with 2- and 4- fold increases in toxicity rates, respectively.⁴⁵ However, the high rates of toxicity in this study have since been questioned.⁴⁶ Only a handful of studies since this 1978 publication have reported INH-related toxicity stratified by alcohol consumption level, and the findings of these subsequent studies have been mixed.^{26,47-51} Thus, data are urgently needed on the safety and tolerability of TB preventive therapy in HIV-infected drinkers to inform worldwide guidelines.⁵²

Adherence to TB preventive therapy among drinkers on ART is unknown. Among those with HIV, alcohol use has been consistently associated with reduced ART adherence,^{22,53,54} and we ([name]) and others have found that alcohol use is associated with discontinuation of active TB treatment.^{23,48,55} Reports of adherence to IPT among all comers range widely, from 19-96%.^{52,56} While completion of 9-months of IPT in a study of persons with HIV in Uganda was 34%,⁵⁶ several studies in HIV-infected persons have shown good completion rates (82%-87%), with the highest rates among those on ART.^{41,57-59} The addition of IPT to an established pill taking routine may be feasible, but adherence to and completion of TB preventive therapy among HIV-infected drinkers on ART is not known.

Valid measurement of medication adherence is critical to evaluating IPT. A key component of the scale up of TB preventive therapy for persons with HIV will ultimately be medication adherence. Self-reported adherence measures have limitations,⁶⁰⁻⁶³ especially in settings in which socially desirable responses are likely to be high. This problem was recently illustrated by the lack of efficacy of pre-exposure prophylaxis for HIV in a large trial, due to patients' misreporting taking the prescribed antiretrovirals.⁶⁴

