The target population will be HIV/TB-infected men and women who are either current drinkers (past 3 months, n=200) or non-drinkers (no alcohol in the past year, n=100), who meet screening criteria (i.e. ≥ 18 years old, on ART, TST positive, no history of prior active TB, live within 2 hours travel time of the study site), and are patients of the Mbarara Regional Referral Hospital (MRRH) Immune Suppression Syndrome (ISS) Clinic. This study will build on the foundation of the Uganda ARCH cohort, including its predecessor cohort as well. We will contact Uganda ARCH study participants (which included drinkers and non-drinkers) to determine their current eligibility for the proposed study. Those who are eligible and interested will be enrolled in the study of TB preventive therapy and receive continued follow-up as part of the Uganda ARCH cohort within the URBAN ARCH consortium. We will enroll additional participants recruited from the ISS Clinic, as needed, to meet our enrollment targets. A screening phase will include blood testing to test liver enzymes (ALT and AST) to rule out patients with elevations ($>2x$ the upper limit of normal [ULN]), and to rule out active TB (symptom screening, and if symptomatic: AFB and Xpert MTB/RIF testing and chest X-ray if not pregnant). Once considered eligible for the study, INH and pyridoxine (vitamin B6) will be dispensed and the study will include regular assessments of hepatotoxicity and other side effects, measures of medication adherence, assessment of drinking, and collection of dried blood spots (DBS) for PEth and small hair samples (approximately 100 hair fibers) for PEth and INH concentration, respectively. After the course of INH (6 months, daily) is completed, study participants will participate in twice yearly study visits as part of the continued cohort. The follow-up cohort study visits will include a survey, symptom assessment and follow-up testing as needed to detect active TB, and blood collection for DBS for PEth, and storage in the URBAN ARCH repository. Baseline blood testing will also include tests for hepatitis B surface antigen, confirmation of HIV status, CD4 cell count, and HIV viral load.

NIH-REQUIRED PROGRESS REPORT

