(mild/moderate) ALT/AST elevations (2-5x the upper limit of normal [ULN]), and none had Grade 3 elevations (≥ 5 times the ULN); there was no difference by drinking status ($p=0.90$). ALT/AST elevations were also low in our study of alcohol biomarkers in Ugandan HIV-infected drinkers ($n=77$).³⁰ These very low levels of underlying liver injury among HIV-infected drinkers in Uganda, suggest that they are at low risk for hepatotoxicity.

Under-report of alcohol consumption. We ([name]) have repeatedly found evidence of under-reporting of alcohol consumption in several studies conducted among persons with HIV in Uganda.^{81,93,96} For example, we found a doubling of self-reported alcohol use when specimen collection for alcohol biomarkers was introduced into an ongoing cohort study.⁹⁶ In another study, we conducted PEth testing on stored specimens, and found of those with quantifiable PEth, over half had denied prior month alcohol use.⁹³ Objective measurement of alcohol consumption is needed; we will use PEth levels as a biological marker of heavy alcohol consumption.

Reductions and rebounds in alcohol use over one year. We ([name]) studied heavy alcohol consumption, defined as AUDIT-C positive or PEth ≥ 50 ng/ml, during the first year of HIV care and found a significant interaction with ART use, such that there was a decline in heavy drinking prior to ART start (per-month adjusted odds ratio [AOR] 0.91; 95% confidence interval [CI]: 0.83-0.99), but increases after ART start (per-month AOR 1.11; 95% CI: 1.01-1.22).⁸¹ Thus, drinkers may reduce alcohol use when advised to, but heavy drinking often rebounds. Repeated objective measurement of alcohol use will be needed to determine whether drinkers can reduce their alcohol use for the duration of a 3- or 6- month course of TB preventive therapy.

Alcohol use leads to poorer TB treatment adherence In a retrospective cohort of 225 patients who received treatment for multi-drug resistant (MDR) TB in South Africa, we ([name]) found that self-reported recent alcohol use led to increased risk of treatment discontinuation (adjusted HR=2.1, CI 1.1-4.0, $p=0.02$).²³ This work supports that alcohol is a particularly important variable in predicting poor TB treatment completion.

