(5) The eligibility criterion for the proposed study is current (prior 3 month) drinking OR non drinking in the prior year, while the WHO recommendations refer to “regular and heavy alcohol consumption”. We will use “current drinking” because we have found that while half of current drinkers report heavy drinking by the AUDIT-C criteria (52%), a large proportion of current drinkers (21%) have high PEth levels (≥ 50 ng/ml) but do not report heavy drinking (Table 2, above). Thus, an eligibility criterion of current drinking will allow us to examine toxicities among drinkers who do not fully report their level of drinking so that future guidelines can account for under-reporting of drinking.

C.3.3 Study setting and eligibility. This study will be conducted in the Immune Suppression Syndrome (ISS) HIV Clinic of the Mbarara Regional Referral Hospital (MRRH) at MUST, the site of the Uganda ARCH. There are over 12,000 active patients at the ISS Clinic. The ISS Clinic and pharmacy use electronic medical records (EMR) via the Open Medical Record System (OpenMRS). Eligibility criteria will be: ISS clinic patient age ≥ 18 , living within 2 travel hours of the clinic, fluent in Runyankole or English, on ART, and self-reported alcohol consumption in the prior 3 months or abstainer. Exclusion criteria will be as follows: plans to move in the coming 6 months, on nevirapine (NVP, an ART drug that is declining in usage due to high risk for hepatotoxicity), history of active TB, current active TB, prior TB preventive therapy, and ALT or ALT elevation ($>2x$ ULN).

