C.3.5 Intervention. The study intervention will include a single arm given (1) 6H: 300 mg INH daily for 6 months. All participants will also receive 25 mg pyridoxine (vitamin B-6) daily for the treatment duration to reduce the risk of INH-induced peripheral neuropathy.¹¹¹ Patients will be encouraged to continue taking all other concurrently prescribed drugs (i.e., ART and cotrimoxazole). Patients will receive adherence advice, advice to avoid hepatotoxic substances (e.g. acetaminophen, alcohol, herbal medicines), instructions on monitoring side effects, phone numbers for contacting the medical staff in case of serious side effects, and instructions on using the EMM bottle like a regular medicine bottle. The pills will be dispensed at the pharmacy where the participants receive their ART.

C.3.6 Follow-up study visits. Assessments for toxicity will occur week 2 and months 1 through 7 (Table 3). A clinical officer will screen for symptoms of hepatotoxicity and other side effects using a Case Report Form (CRF) based on the TEMPRANO ANRS adverse event grading⁶ and perform ALT/AST testing. Treatment will be stopped if a patient develops a Grade 3/4 toxicity, as determined by the study physician. In addition, the monthly study visits while on medication will include pharmacy pill counts, EMM data downloads, and brief surveys on alcohol use and adherence. Hair collection will occur at 3 and 6 months. Blood collection will occur at baseline (for PEth, CD4 cell count, HIV viral load, and repository storage), 3 and 6 months, and every 6 months thereafter. Participants will also be given a card with phone numbers to contact the clinical staff if side effects occur between study visits; if side effects occur, participants will be asked to come in for additional ALT/AST testing and follow-up. These calls and visits will also be recorded in a CRF. All CRFs will be reviewed weekly by the study physician. Screening for symptoms for active TB, and sputum testing and chest X-ray if symptoms are reported, will occur at every follow-up visit, including those after the completion of the trial. High retention will be maintained as in our prior studies using follow up phone calls, alerts when patients come to the ISS clinic, and home visits when needed.

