C.3.7 Data management. Data management and quality assurance will be jointly led by the UCSF and the BU Data Coordinating Center (DCC). As in the previous studies, tracking information will be entered into a database which will generate reminders for follow-up visits. The tracking database will also be used to automatically randomize patients to study arms. The questionnaire data, brief assessments, laboratory results, and the CRF data will be entered directly into a laptop computer in Uganda while offline, and later uploaded to a secure server at UCSF. The EMM adherence data will be uploaded weekly to a secure website, cleaned, and merged with the other study data. All data will undergo weekly checks for completeness and range criteria.

C.3.8 Measurements.

Safety and tolerability. Safety will be assessed by the occurrence of a Grade 3/4 hepatotoxicity at any time during the assigned treatment period. Lack of tolerability will be defined as any treatment discontinuation prior to completion of the prescribed course due to side effects or ALT/AST elevations.

Adherence. We will measure medication adherence using EMM, pharmacy pill count, self-report, and INH concentration in hair. While there is no gold standard for determining medication adherence, EMM adherence has been highly predictive of undetectable HIV viral load¹¹²⁻¹¹⁴ is considered the reference standard,^{62,112,115,116} and therefore will be our primary measure of adherence. EMM adherence will be defined as the number of pill bottle openings (no more than 1 per day counted)¹¹³ divided by the number of prescribed doses over the study period. Adherence to vitamin B-6, which will be provided in a separate bottle, will not be part of the adherence measurement.

Self-reported adherence measures will include the visual analog scale (VAS) which asks the patient to identify their past month percent adherence on a visual scale that ranges from 0 to 100%, and the Self Rating Single Item (SRSI) adherence scale,^{117,118} which asks participants to rate their ability to take their medications as prescribed over the past month.¹¹⁹ Both of these measures are brief¹¹⁸ and are strong predictors of viral suppression.¹¹⁸ Lastly, we will collect hair samples at 3 months and 6 months, and will measure the INH concentration (ng/mg) in the hair.

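### Table 1, the only place where the primary endpoint's thresholds are written out, omits AST from the symptomatic limb, and the C.3.3 exclusion repeats the slip

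*Combined protocol and SAP*

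**What the plan says.** Table 1 (frequently used acronyms and definitions) gives Grade 3/4 hepatotoxicity as "ALT or ALT >3 x ULN and symptoms (nausea, vomiting, jaundice, or fatigue) OR ALT or AST >5 x ULN". It has two limbs: a lower enzyme threshold that requires symptoms, and a higher one that does not.

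C.3.8 makes this term the safety outcome: "Safety will be assessed by the occurrence of a Grade 3/4 hepatotoxicity at any time during the assigned treatment period". C.3.9 makes its incidence among current drinkers the primary analysis, with an exact binomial interval. Neither section restates thresholds.

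For eligibility, C.3.3 excludes people with "ALT or ALT elevation ($>2x$ ULN". The Study Design Overview describes the same screen as "blood testing to test liver enzymes (ALT and AST) to rule out patients with elevations" above 2x ULN, and C.3.12 also describes baseline screening on ALT/AST at that cut-off.

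At follow-up visits, C.3.6 has the clinical officer screen for symptoms "using a Case Report Form (CRF) based on the TEMPRANO ANRS adverse event grading" and "perform ALT/AST testing". The same section stops treatment for a Grade 3/4 toxicity as determined by the study physician.

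**The concern.** The two limbs of one definition do not cover the same enzymes. An alternative between ALT and ALT has no meaning as a rule, so the symptomatic limb reduces to ALT alone. A programmer who follows Table 1 would leave out one kind of case that the rest of the document treats as liver toxicity: symptoms with AST raised above 3x ULN but not above 5x, and ALT not above 3x.

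Two things are at stake. First, set against an ALT-or-AST reading, the literal endpoint wording can only remove events, never add them. C.3.9 expects about 5 events and compares the rate with published ones, so a single reclassified case shows. Second, C.3.3 and the Study Design Overview give different answers for a person with AST above 2x ULN and ALT not above 2x. That affects who is enrolled. It also affects the number screened out, which C.3.12 uses for its worst-case toxicity rates.

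**Working it through.** **1. Is there another complete definition?** The places that could supply one:

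| Place | Enzymes | Threshold and symptoms |
|---|---|---|
| Table 1, first limb | ALT only, as written | >3x ULN with symptoms |
| Table 1, second limb | ALT or AST | >5x ULN, symptoms not needed |
| C.2, preliminary data | ALT/AST | Grade 3 at 5x ULN or more, no symptom limb |
| C.3.6, CRF | ALT/AST tested | outside scale named, thresholds not reproduced |
| C.3.8 and C.3.9 | not stated for the endpoint | term used without thresholds |
| C.4.2, Aim 3 states | ALT/AST | normal, 3-5x and >5x ULN, each with and without symptoms |

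The C.2 line ("none had Grade 3 elevations (≥ 5 times the ULN") concerns earlier cohort data. Adopting it would drop the symptomatic limb altogether. Table 1 is therefore the only place where the endpoint's thresholds are written out.

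**2. Which cases change status?** Take a symptomatic participant with ALT not above 3x ULN.
- AST not above 3x: a non-event under either reading.
- AST above 3x and up to 5x: a non-event as written, an event under an ALT-or-AST reading.
- AST above 5x: an event under either reading, through the second limb.

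Only the middle row is affected. In the Aim 3 model the same person falls in the symptomatic 3-5x state. C.4.3 says the trial's own data feed that model, so Aims 1 and 3 would classify this person differently.

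**3. Eligibility.** With AST above 2x ULN and ALT not above 2x, a person is eligible under C.3.3 as written and ruled out under the Study Design Overview. C.3.12 agrees with the Overview.

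**4. The plan's own precision figure (C.3.9).** Evaluable drinkers: 200 x 0.90 = 180. Expected events: 180 x 0.026 = 4.68, about 5. Exact (Clopper-Pearson) limits for x events in n:
- lower = 2.5% quantile of Beta(x, n - x + 1)
- upper = 97.5% quantile of Beta(x + 1, n - x)

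With x = 5 and n = 180 this gives 0.91% to 6.36%, length 5.46%. C.3.9 states 0.9% to 6.4% and 5.5%, so the figure is reproduced. It does not depend on the ALT/AST wording.

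**5. Illustration of size.** The documents give no share of AST-only symptomatic events in the affected band, so k is an assumption. If 5 events occur under an ALT-or-AST reading and k of them are of this kind, the literal wording yields (5 - k)/180:

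| k | Events counted | Estimate | 95% exact CI |
|---|---|---|---|
| 0 | 5/180 | 2.78% | 0.91 to 6.36 |
| 1 | 4/180 | 2.22% | 0.61 to 5.59 |
| 2 | 3/180 | 1.67% | 0.35 to 4.79 |
| 3 | 2/180 | 1.11% | 0.13 to 3.96 |

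Each omitted case lowers the estimate by 1/180 = 0.56 percentage points, which is 1/5 = 20% of the expected numerator.

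**The case against.** The strongest reply is that this is an obvious typing error whose intent is easily recovered. The second limb on the same line names both enzymes, as do the screening, follow-up, tolerability and modelling text. Anyone coding the endpoint would have to write the same test twice without noticing. The study physician's determination in C.3.6 may also catch such cases. Much of this stands: the practical risk is limited. But the same slip occurs in two separate operative places, and the plan does not say whether the physician's call, the CRF scale or Table 1 governs the analysis endpoint.

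A reader might also infer more than the documents support:
- *That every AST-only symptomatic event is lost.* It is not; AST above 5x ULN counts under the second limb.
- *That the reported rate will be too low.* The endpoint wording can only remove events, but the number removed may be zero. If C.3.3 were also followed literally, people with raised baseline AST could be enrolled and might plausibly add events. The net direction is not established.
- *That the missed endpoint case and the wrongly enrolled person are the same.* They are separate: one is an on-treatment event between 3x and 5x ULN with symptoms, the other a baseline value above 2x ULN.
- *That the sample-size or precision statement is wrong.* It is not.

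The intervals in the illustration also overlap heavily, so one or two omitted cases would not by themselves change the broad conclusion.

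**Conclusion.** The point holds in a narrow form. As written, the primary endpoint omits symptomatic cases with AST above 3x and up to 5x ULN and ALT not above 3x. C.3.3 admits people with AST above 2x and ALT not above 2x whom the Study Design Overview rules out. The likely cause is typographical and the intended reading can be inferred, but the text is operative and the primary analysis rests on about 5 expected events.

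The size is unknown from the documents. It is 0.56 percentage points per affected case on 180 evaluable drinkers, and nothing if no such case occurs. The illustration assumes 5 events under an ALT-or-AST reading and an arbitrary k. This should be corrected before events are classified; it does not call for redesign or a new sample size.

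**What to change.** Before any event is classified:

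1. Reconcile the symptomatic limb in Table 1 with its second limb and with the ALT/AST wording in C.3.6 and C.4.2.
2. Reconcile the C.3.3 exclusion with the Study Design Overview and C.3.12. Count those screened out under the one reconciled rule, because that number feeds the worst-case rates.
3. Derive the analysis endpoint in code from the recorded ALT, AST and symptom fields, using the one reconciled definition.
4. Reconcile C.3.6 as well, since stopping of treatment depends on the same Grade 3/4 term, and state how the CRF grading and the study physician's determination relate to the analysis endpoint. Which clinical rule should apply is for the investigators; none is proposed here.

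The cost is a few corrections to wording and a short derivation specification. C.3.6 and Table 3 already provide for symptom assessment and ALT/AST testing at every toxicity visit, so no new data are needed.

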(1) The primary outcome of this study is safety only, rather than the standard drug trial outcomes of safety and efficacy. We made this decision because, while a study examining the efficacy of TB preventive therapy for HIV-infected drinkers would be valuable, such a study would require thousands of participants and would be premature if safety cannot be established. Because the WHO guidelines exclude heavy drinkers due to safety concerns, we felt that careful examination of safety and tolerability would be a key contribution to the development of an evidence-based global recommendation on how to give TB preventive therapy to HIV-infected alcohol users in resource constrained settings.

(2) We decided not to include an untreated control group, because we will be meeting the U.S. standard of care of providing TB preventive therapy to drinkers with ALT/AST monitoring.⁴⁴ Given the known reductions in morbidity and mortality of TB preventive therapy for persons with HIV, and the safety of this treatment when monitoring is conducted, an untreated control group would represent a lower level of care provision with questionable ethics.⁴⁴ In addition, it will not be necessary to have an untreated control group to determine the level of ALT/AST elevations without therapy, because we will have an estimate of the background level of elevations in this cohort of drinkers via baseline testing.

(3) We will include only participants with positive tuberculin skin test (TST) results. TB preventive therapy is more effective for persons with HIV who are TST positive,⁷ although the WHO recommends providing IPT to all persons with HIV in resource limited settings because skin testing is often not available⁹ and may have lower sensitivity.¹⁰⁴ However, in the research setting, TST testing is possible and we will limit our study population to TST positive participants who represent those most at risk for developing TB in this population.

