TB epidemiology. The simulation model generates a cohort using the distribution in the target population of age, sex, prevalence of positive TSTs (>5 mm induration), and prevalence of sub-clinical (asymptomatic, so not identified) active TB. We will stratify all demographic and epidemiologic parameters by level of self-reported alcohol use at baseline, as above (any current drinking, heavy drinking, and very heavy drinking – see C.3.9), using the AUDIT-C that is available to treating clinicians in the real-world.

TB preventive therapy. The simulation of TB preventive therapy includes treatment discontinuation due to hepatotoxicity, as well as poor adherence or default. The model is structured to simulate any TB preventive treatment regimen. All parameters related to TB preventive therapy are regimen-specific and we will stratify them by level of alcohol use. We will model the benefits of TB preventive therapy as a relative reduction in the

Table 4: Select model parameters for decision model proposed in Aim 3.

	Parameter estimates	Data source
TB epidemiology		
Age/sex demographics		ADEPTT
Prevalence reactive TST		ADEPTT
Prevalence subclinical TB at baseline	0.085-0.094	135,136
Level of alcohol use prior to therapy		ADEPTT
TB preventive therapy		
Transitions between AST/ALT categories		ADEPTT
Probability of symptoms by AST/ALT	0.35	137
Toxicity-related mortality by AST/ALT	0.0-0.05	137-139
Adherence		ADEPTT
Health state utility for those with hepatotoxicity	0.65-1.0	140
Health state utility for those w/o hepatotoxicity	0.82-1.0	140
Progression to TB and TB mortality		
Incidence TB (per 100 person-years)		141-143
TST positive	3.41	
TST negative	3.06	
Hazard ratio for active TB		144-147
100% adherence vs. no therapy	0.11-0.41	
Partial (50%) therapy vs. no therapy	0.25-0.91	
TB-related case-fatality proportion	0.23	148
Health state utility with active TB	0.66-0.85	140
HIV and other non-TB mortality		
Life expectancy (starting age 31) CD4 >500	66 years	149-152
Standardized mortality ratio by CD4 count		151-154
CD4 350-499 cells/mm ³	3.5	
CD4 200-349 cells/mm ³	5.6	
CD4 <200 cells/mm ³	30.3	
Health state utility for HIV-infected persons	0.62-1.0	155-157

rate of progression to active TB. In the model, patients with sub-clinical TB do not benefit from the preventive therapy.

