Progression to active TB and death. Individuals in the simulation model will have a monthly probability of developing active TB that is stratified by drinking status.^{141,158} Those who develop active TB experience increased mortality and decreased quality of life. In addition, a portion of simulated patients with active TB will develop drug resistant disease, characterized by longer treatment courses, higher mortality, and lower quality of life than drug sensitive disease. We will model the effectiveness of TB preventive therapy as a relative reduction in the rate of developing active TB. A complete course of 6H provides a 30-50% reduction in reactivation,⁴⁻⁸ with a larger absolute reduction in TB incidence among those who have reactive TST than in those who do not. Studies among HIV-infected persons in settings of TB incidence, similar to Uganda, demonstrate that the benefits of TB preventive therapy are durable for five years.^{145,159} We will therefore model a 5-year reduction in the incidence of active TB, followed by a rapid return to the baseline TB incidence.

Competing risks of death Individuals in the existing model have an age- and sex-stratified risk of death from causes other than TB. In this proposed analysis of TB preventive therapy in HIV-infected persons in Uganda, the competing risks of death will reflect mortality related to HIV infection and all other non-TB mortality.

C.4.3 Data sources for the model. Whenever possible, we will use the novel data from Aims 1 and 2 of this study (Table 4, denoted as ADEPTT) for model parameters. Other model parameters will be obtained from the medical literature.

TB epidemiology. The ADEPTT cohort will inform the age and sex distributions, and the prevalence of reactive TST (>5 mm) at baseline and level of self-reported alcohol use. We will use published reports of the prevalence of subclinical TB from established African cohorts.^{135,136}

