TB preventive therapy. The ADEPTT study includes frequent assessment of ALT/AST and symptoms. These data, stratified by level of self-reported alcohol consumption, will inform all of the parameters governing movement between toxicity-related health states. Because the study will stop treatment at the identification of any Grade 3/4 hepatotoxicity, we anticipate no medication-related deaths in ADEPTT. Therefore, we will use the medical literature to inform mortality from each toxicity-related health state in the model, as well as the health state utility of patients with toxicity-related symptoms.¹³⁷⁻¹⁴⁰

Progression to active TB and death. Because the number of observable cases of active TB in the cohort after therapy is expected to be low, we will use the medical literature to inform the incidence of active TB, stratified by TST status, without preventive therapy,¹⁴¹⁻¹⁴³ and will account for the reported efficacy of TB preventive therapy.¹⁴⁴⁻¹⁴⁷ We will use reports of health state utility with active TB collected in SSA.¹⁴⁰

Competing risks of death. We will estimate mortality from all causes other than TB using long-term follow-up of cohorts of HIV-infected persons in SSA. We will use the literature to estimate non-TB mortality among a cohort of HIV-infected persons on ART in SSA with baseline CD4>500¹⁴⁹⁻¹⁵² and published reports of the HR for mortality by lower CD4 counts.¹⁵¹⁻¹⁵⁴ We will also use the medical literature to estimate health state utilities for HIV-infected individuals with and without TB.

C.4.4 Aim 3 analyses. We will use the model to simulate the long-term outcomes of a cohort of HIV-infected drinkers in Uganda with demographic and clinical characteristic similar to those of the ADEPT-TB cohort assuming that TB preventive therapy is provided to all HIV-infected patients who drink alcohol using each of the following TB preventive therapy and monitoring strategies:

- (1) No therapy (standard of care)
- (2) TB preventive therapy without hepatotoxicity monitoring unless patient is symptomatic (no monitoring)
- (3) TB preventive therapy with hepatotoxicity monitoring at week 2 of therapy only (week 2 monitoring)
- (4) TB preventive therapy with hepatotoxicity monitoring monthly throughout (monthly monitoring)

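### Aim 3 splits untreated TB incidence by TST result but lists no TST-specific efficacy, although C.3.2 says therapy works better in TST-positive people

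*Combined protocol and SAP*

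**What the plan says.** C.3.2 item (3) sets the enrolment rule, "We will include only participants with positive tuberculin skin test (TST) results", and supports it with the statement that "TB preventive therapy is more effective for persons with HIV who are TST positive", citing a systematic review of randomised trials (reference 7). It gives neither a size nor a scale for that difference.

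The Aim 3 model handles TST as follows:

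- **Cohort.** C.4.2 generates the simulated cohort using, among other inputs, the "prevalence of positive TSTs (>5 mm induration". A TST-negative stratum is therefore provided for.
- **Untreated risk.** Table 4 gives TB incidence of 3.41 per 100 person-years if TST positive and 3.06 if TST negative. C.4.3 confirms that incidence without therapy is stratified by TST.
- **Efficacy.** C.4.2 models benefit as a relative reduction in progression to active TB and says "All parameters related to TB preventive therapy are regimen-specific and we will stratify them by level of alcohol use". The Table 4 row "100% adherence vs. no therapy" shows 0.11-0.41, and the row for partial (50%) therapy shows 0.25-0.91. Neither is split by TST.
- **Expected TST difference.** The C.4.2 paragraph on progression says "A complete course of 6H provides a 30-50% reduction in reactivation", "with a larger absolute reduction in TB incidence among those who have reactive TST than in those who do not".
- **Who is treated.** C.4.4 assumes "TB preventive therapy is provided to all HIV-infected patients who drink alcohol", in a cohort resembling the trial's.

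**The concern.** The plan treats TST status as important enough to efficacy to restrict enrolment. It then describes a benefit model in which TST changes only the untreated rate. If C.3.2 means a larger relative effect in TST-positive people, which is its most natural reading, the model as described does not contain it.

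This matters because C.4.4 first compares therapy without monitoring against no therapy, and C.3.2 itself notes that skin testing is often unavailable in such settings. Untested drinkers are a mix of TST-positive and TST-negative people. Both carry the toxicity risk, so the balance for TST-negative people depends on the efficacy assumed for them. Varying overall efficacy in the probabilistic analysis (C.4.5) does not address this: with a common hazard ratio, every draw keeps the same ratio of benefit between the two groups.

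**Working it through.** The plan states no Aim 3 output by TST status, so there is no figure of its own to reproduce.

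**Step 1: what a common hazard ratio implies.** Absolute rate reduction = incidence x (1 - HR), with incidence from Table 4.

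| HR | TST positive, per 100 person-years | TST negative, per 100 person-years |
|---|---|---|
| 0.11 | 3.41 x 0.89 = 3.03 | 3.06 x 0.89 = 2.72 |
| 0.41 | 3.41 x 0.59 = 2.01 | 3.06 x 0.59 = 1.81 |
| 0.50 | 1.71 | 1.53 |
| 0.70 | 1.02 | 0.92 |

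The factor (1 - HR) cancels, so the ratio is 3.06/3.41 = 0.90 at every HR (inverse 1.11). The larger absolute reduction that C.4.2 expects in TST-positive people then comes from baseline incidence alone and is an 11% difference.

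**Step 2: illustration if the listed HR is a TST-positive one.** Inputs from the documents: incidence as above, case fatality 0.23 (Table 4), five years of protection (C.4.2), and TST-positive HR 0.26, the midpoint of 0.11 and 0.41. Assumptions: TST-negative HR 0.7 to 1.0 (not in the documents); TST-positive share of one-third (borrowed from the worldwide latent-infection floor in section B) to 60% (no source); full adherence; no competing deaths; no subclinical TB.

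Five-year risk = 1 - exp(-5 x rate). Cases averted per 1,000:

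- TST positive, HR 0.26: 156.8 - 43.4 = 113.4
- TST negative, HR 0.26: 141.9 - 39.0 = 102.9
- TST negative, HR 0.7: 40.3
- TST negative, HR 1.0: 0

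TB deaths averted per 1,000 = 0.23 x the share-weighted cases averted. At a one-third share with a common HR: 0.23 x (113.4/3 + 2 x 102.9/3) = 24.5.

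| TST-positive share | Common HR 0.26 | TST-negative HR 0.7 | 0.8 | 0.9 | 1.0 | Overstatement |
|---|---|---|---|---|---|---|
| One-third | 24.5 | 14.9 | 12.8 | 10.7 | 8.7 | 1.6 to 2.8 |
| 60% | 25.1 | 19.4 | 18.1 | 16.9 | 15.6 | 1.3 to 1.6 |

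The text of C.4.2 gives a 30-50% reduction (HR 0.50-0.70). Using its midpoint of 0.60 instead of 0.26, the factor runs from about 1.1 to 2.8.

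**Step 3: illustration if the listed HR is pooled over the same TST mix.** Assume half are TST positive, with true HRs of 0.3 (TST positive) and 0.8 (TST negative). The incidence-weighted pooled HR is (0.5 x 3.41 x 0.3 + 0.5 x 3.06 x 0.8) / (0.5 x 3.41 + 0.5 x 3.06) = 0.536. Five-year cases averted per 1,000:

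- TST positive: 69.3 modelled v 106.9 true
- TST negative: 63.1 modelled v 26.7 true
- Mixed cohort: 66.2 modelled v 66.8 true, ratio 0.99

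Across shares of one-third and one-half, with HR pairs 0.3/0.8 and 0.4/1.0, the mixed-cohort ratio stays at 0.98 to 0.99. The total is nearly right, but each stratum is wrong, in opposite directions.

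**Step 4: an all-TST-positive cohort.** With a TST-positive HR the factor is 1.0. With a pooled HR, benefit is understated, as in the first line of step 3.

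**The case against.** The strongest reply is that the plan never says one hazard ratio will serve both groups. Table 4 is headed as a selection of parameters and shows a range, and stratifying by alcohol level does not rule out also stratifying by TST. This stands: the common hazard ratio is an inference. Still, Table 4, C.4.2 and C.4.3 all provide for TST in incidence and none does so for efficacy, so the specification is at least incomplete.

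Second, *more effective* in C.3.2 may be meant on the absolute scale. The same item calls TST-positive people those most at risk, and C.4.2 speaks of a larger absolute reduction, which any common hazard ratio delivers. This also stands, so no outright contradiction is proved. On the plan's own incidence figures, though, an absolute-only reading amounts to an 11% difference.

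Third, a reader might infer that the model overstates benefit in untested drinkers. The documents do not support that. It requires the Table 4 range to be a TST-positive effect, and neither the TST mix of its sources nor a TST-negative hazard ratio is given. Step 3 shows almost no bias in the total under a matching mix, and step 4 shows that understatement is possible.

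Fourth, it is unclear whether TST-negative people will be simulated. C.4.4 describes a cohort like the trial's, which is all TST positive, alongside therapy for all drinkers and a TST-prevalence input.

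Finally, C.4.5 names efficacy as a candidate for probabilistic analysis. That covers its overall level, not its difference by TST.

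**Conclusion.** The point holds as a gap in the Aim 3 specification, not as a demonstrated bias. What follows from the documents alone is that efficacy is not described by TST although C.3.2 says it differs, and that a common hazard ratio fixes the TST-negative absolute rate reduction at 90% of the TST-positive one. Benefit may then be too high in TST negatives and, with a pooled hazard ratio, too low in TST positives.

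The 1.3- to 2.8-fold figure is conditional on 0.26 applying to TST positives, an assumed TST-negative hazard ratio of 0.7 to 1.0 and an assumed 33-60% TST-positive share. The factor is about 1 if the hazard ratio comes from a similar mix, or if the cohort is all TST positive and the hazard ratio is a TST-positive one. The point concerns Aim 3 only; the primary safety analysis is unaffected. It is worth acting on because the remedy is cheap and settles the matter whichever case applies.

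**What to change.** - In Table 4 and C.4.2, replace the single hazard-ratio rows (full and partial therapy) with separate TST-positive and TST-negative values from the literature. Start with the review cited in C.3.2 (reference 7), if it reports them.
- State the TST mix of each source, and whether TST-negative people are simulated.
- Vary the TST-negative hazard ratio separately, up to 1.0, in the deterministic and probabilistic analyses of C.4.5.
- Report Aim 3 net benefit separately for TST-positive drinkers and for an untested TST mix.
- While revising these inputs, reconcile the Table 4 range (0.11-0.41, a 59-89% reduction) with the 30-50% reduction in C.4.2; the two do not overlap.

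The cost is one more model stratum and additional literature inputs, with no new trial data. Uncertainty for untested drinkers will be wider.
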